4.2. Variable Definitions

4.2.1. Body Mass Index

Body mass index will be calculated as follows:

BMI $(kg/m^2) = [weight (kg)] / [height (m)]^2$.

4.2.2. Prior and Concomitant Medication

Prior medication is defined as any nonstudy medication started before the first dose of INCB050465.

Concomitant medication is defined as any nonstudy medication that is started accordingly:

- Before the date of first administration of INCB050465 and is ongoing throughout the study or ends on/after the date of first study drug administration.
- On/after the date of first administration of INCB050465 and is ongoing or ends during the course of study drug.

A prior medication could also be classified as "both prior and concomitant medication" if the end date is on or after first dose of INCB050465. In the listing, it will be indicated whether a medication is prior-only, concomitant-only, or both prior and concomitant medication.

For the purposes of analysis, all medications will be considered concomitant medications unless the medications can unequivocally be defined as not concomitant.

5. STATISTICAL METHODOLOGY

5.1. General Methodology

Unless otherwise noted, SAS® software (SAS Institute Inc, Cary, NC; Version 9 or later) will be used for the generation of all tables, graphs, and statistical analyses. Descriptive summaries for continuous variables will include, but not be limited to, the number of observations, mean, standard deviation, median, minimum, and maximum. Descriptive summaries for categorical variables will include the number and percentage of subjects in each category.

Interim analyses are planned for this study as defined in Section 9.

5.2. Treatment Groups

This is a Phase 2, multicenter, international, and open-label study. The study consists of 2 groups: Group A and Group B. In Group A, 100 subjects who were not previously treated with a BTK inhibitor (eg, ibrutinib) will be enrolled. In Group B, up to 20 subjects who were previously treated with a BTK inhibitor (eg, ibrutinib) will be enrolled. Data from Group A and Group B will be analyzed separately.

5.3. Analysis Populations

5.3.1. Full Analysis Set

The full analysis set includes all subjects enrolled in the study who received at least 1 dose of INCB050465.

The full analysis set will be used for the summary of demographics, baseline characteristics, subject disposition, and analyses of all efficacy data.

5.3.2. Per Protocol Population

The PP population includes all subjects in the full analysis set who were compliant with the Protocol.

The following procedures will be performed to identify those subjects who are to be excluded from the PP population before the database freeze:

- Clinical review of Protocol deviations
- Clinical review of concomitant medications as defined in Section 5.6 of the Protocol
- Clinical review of the dose administration and drug accountability listing

The determination of subjects being considered for exclusion from the PP population by the clinical team will be prepared and signed before database freeze.

5.3.3. Safety Population

The safety population includes all subjects enrolled in the study who received at least 1 dose of INCB050465.

All safety analyses will be conducted using the safety population.

6. BASELINE, EXPOSURE, AND DISPOSITION VARIABLES AND ANALYSES

Appendix A provides a list of data displays. Sample data displays are included in a separate document.

6.1. Baseline and Demographics, Physical Characteristics, and Disease History

6.1.1. Demographics and Baseline Disease Characteristics

The following demographics will be summarized and listed for the full analysis set: age, sex, race, ethnicity, weight, height, and BMI. ECOG performance status at baseline will be summarized and listed for the full analysis set.

6.1.2. Disease History

Time since diagnosis, initial disease type, time since transformation to DLBCL, stage at initial diagnosis, NCCN international prognostic index, current DLBCL subtype, current diagnosis type, current stage, presence of B-symptoms, and tumor markers will be summarized and listed for all subjects in the full analysis set.

Time since diagnosis will be calculated as follows:

Time since diagnosis (years) = (Day 1 date – date of diagnosis + 1) / 365.25.

Time since transformation to DLBCL will be calculated as follows:

Time since transformation (years) = (Day 1 date – date of transformation + 1) / 365.25.

6.1.3. Prior Cancer Therapy

Number of prior systemic cancer therapy regimens will be summarized for all subjects in the full analysis set. The component drugs of prior systemic therapy regimens will be coded using the WHO Drug Dictionary. Number and percentage of subjects with each drug will be summarized by WHO drug class and WHO drug preferred term. Regimen name, component drugs, start and stop date, route of the medication, best response, reason for discontinuation, and date of relapse/progression will be listed.

Number of subjects who received prior radiation will be summarized for the full analysis set.

Number of subjects who had prior surgery or surgical procedure for cancer treatment will be summarized for the full analysis set. Date and description of the surgery/procedure will be listed.

Number of subjects who had prior hematopoietic stem cell transplant will be summarized for the full analysis set. Date of transplant, type of transplant, source of cells, line of therapy, best response, date of relapse/progression, and drug used with the transplant will be listed.

6.1.4. Medical History

Medical history will be coded to SOC and PT using MedDRA coding dictionary. For subjects in the full analysis set, medical history will be summarized by SOC and PT and listed.

6.2. Disposition of Subjects

The number and percentage of subjects who were treated, discontinued study treatment with a primary reason for discontinuation, and discontinued from the study with a primary reason for withdrawal will be summarized and listed for the full analysis set.

The number of subjects enrolled by country and site will also be provided for the full analysis set.

6.3. Protocol Deviations

Protocol deviations recorded on the CRF will be presented in the subject data listings.

6.4. Exposure

For subjects in the safety population, exposure to INCB050465 will be summarized descriptively as the following:

- **Duration of treatment with INCB050465 (days):** Date of last dose of study drug date of first dose of study drug + 1.
- Duration of treatment with INCB050465 for initial QD schedule (days): Date of last dose of study drug during initial QD schedule date of first dose of study drug + 1.
- **Duration of treatment with INCB050465 for QW schedule (weeks):** Ceiling of [(date of last dose of INCB050465 during QW schedule date of first dose of INCB050465 during QW schedule + 1) / 7].
- Average reported daily dose of INCB050465 for initial QD schedule (mg/day): Total reported INCB050465 dose taken during initial QD schedule (mg) / duration of treatment with INCB050465 for initial QD schedule (days).

- Average reported weekly dose of INCB050465 for QW schedule (mg/week): Total reported INCB050465 dose taken during QW schedule (mg) / duration of treatment with INCB050465 for QW schedule (weeks).
- **INCB050465 dose modifications:** Number of subjects who had INCB050465 dose reduction and interruption will be summarized for initial QD schedule, QW schedule, and overall.

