
Study Schedule/Procedures: During screening and every 21 days from the date of first study drug administration (Day 1), a study visit will be conducted that includes a physical examination, clinical laboratory tests, and an assessment of AEs. [REDACTED]
 
[REDACTED]
 
During screening, subjects will have an objective assessment of disease status performed by fluorodeoxyglucose (FDG) positron emission tomography (PET) and diagnostic quality CT scan or MRI. Subjects will also have a bone marrow biopsy performed at screening unless the subject has FDG-avid disease or has undergone a recent bone marrow biopsy. Disease status will be subsequently assessed by PET-CT/MRI at Weeks 9, 18, 27, and every 18 weeks thereafter until disease progression. On-study bone marrow biopsies will be required only if needed to confirm a CR/CMR.
 
Subjects withdrawn from study treatment for reasons other than disease progression will be followed for disease assessment until either radiologic disease progression, the start of a new anticancer therapy, or death (whichever occurs first).
 
Subjects withdrawn from study treatment because of disease progression will be followed approximately every 12 weeks for subsequent anticancer therapies and survival.
 
Note: With Amendment 4, Protocol-required procedures have been reduced for ongoing subjects.

Estimated Duration of Participation: Subject participation through safety follow-up is expected to average approximately 11 months, which includes the following:
 

• A screening period lasting up to 28 days.

• A treatment period lasting as long as the subject is receiving benefit, tolerating the regimen, and has not met withdrawal criteria (approximately 9 months).

• A safety follow-up period lasting 30 to 35 days.

 
Subjects will be followed for approximately 12 months after the safety follow-up period.

Estimated Number of Subjects: The target enrollment for this study is 100 to 120 subjects.

Principal Coordinating Investigator: [REDACTED], MD, [REDACTED]

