### **5.2.4. Instruction to Subjects for Handling INCB050465**

The subject must be instructed in the handling of study drug as follows:

- To store study drug at room temperature.
- To remove from the study drug bottle only the number of tablets needed at the time of administration.
- Not to remove doses in advance of the next scheduled administration.
- To make every effort to take doses on schedule.
- To report any missed doses.
- To keep INCB050465 in a safe place and out of reach of children.
- To bring all used and unused study drug kits to the site at each visit.

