**Table 3: Dose Levels for INCB050465**

Timepoint	Dose
Starting dose	20 mg once daily for 8 weeks
Week 9, Day 1	20 mg once weekly
First dose reduction	10 mg once weekly
Second dose reduction	5 mg once weekly

Note that the first dose reduction is applicable for subject receiving either 20 mg QD or 20 mg once weekly.

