**Table 4: Schedule of Assessments**

**Note: Upon implementation of Protocol Amendment 4, only the schedules of assessments in Table 6 and Table 7 should be followed.**

Procedure	Section	Screening	Treatment				EOT	Safety Follow-Up	Disease Follow-Up	Survival Follow-Up
		Day -28 to -1	Day 1	Day 15 (± 3 Days)	Every 3 Weeks (± 3 Days)	Every 12 Weeks (± 3 Days)		EOT + 30-35 Days		Every 12 Weeks (± 1 Week)
Informed consent	7.1	X								
Contact IWRS	7.2	X	X		X		X			
Inclusion & exclusion criteria	3.1 3.2	X	X							
Demography and medical history	7.3.1	X								
Prior/concomitant medications	7.3.1.1	X	X	X	X		X	X		
Comprehensive physical exam	7.4.2	X a					X			
Disease-specific physical exam	7.4.2.1		X	X	X			X		
Vital signs	7.4.3	X	X	X	X		X	X		
12-lead ECG	7.4.4	X	X	X		X	X	X		
ECOG status	7.5.6	X	X		X		X	X		
AE assessment	7.4.1	X	X	X	X		X	X		
FDG-PET/CT scan	7.5.1 7.5.2	X	Every 9 weeks (± 1 week) through Week 27, then every 18 weeks (± 1 week) thereafter. b							
Bone marrow exam	7.5.3	X c								
Study drug dispensing	5.1		X		X d					
Study drug accountability	5.3		X		X		X			
INCB050465 administration	5.2.1		X	X	X					
Disease follow-up	6.4.2								X e	
Survival follow-up	6.4.3									X f

FDG = fluorodeoxyglucose; PET = positron emission tomography.

a Height required at screening only.

b If the PET-CT is of diagnostic quality, then a separate CT does not need to be performed. If CT is not available, is not practicable, or is contraindicated, then an MRI may be substituted. Every effort must be made to use the same modality for disease assessment throughout the study for each individual subject.

c Required at baseline except for reasons provided in Section 7.5.3. Also required if needed to confirm CR/CMR.

d Study drug will be dispensed at Weeks 1, 4, 7, and 10, and every 12 weeks thereafter.

e Only for subjects who discontinue study treatment for reasons other than disease progression.

f May be conducted by phone or email.

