3. STUDY DESIGN

This is a Phase 2, multicenter, international, open-label study designed to evaluate the safety and efficacy of INCB050465 20 mg QD for 8 weeks followed by 20 mg QW. The study drug will be administered orally to subjects with relapsed or refractory DLBCL (see Figure 1). The study consists of 2 groups: Group A and Group B. In Group A, 100 subjects who were not previously treated with a BTK inhibitor (eg, ibrutinib) will be enrolled. In Group B, up to 20 subjects who were previously treated with a BTK inhibitor (eg, ibrutinib) will be enrolled. Subjects will be evaluated for ORR by an IRC and followed for DOR, PFS, and OS. Subjects may receive treatment until disease progression, death, unacceptable toxicity, or consent withdrawal. An interim futility analysis is planned when the first 40 subjects in Group A have been treated and have been evaluated for response or have permanently discontinued study treatment because of disease progression, withdrawal of consent, or death. Group A of the study will be terminated for futility if \leq 13 of the 40 subjects have responded (ie, CR/CMR or PR/PMR) based on assessments provided by the IRC; otherwise the study will continue. No formal futility analysis will be conducted for Group B.

Figure 1: Study Design

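### SAP 6.4: rounding up the weekly-schedule duration loses a whole week when the first-to-last dose interval is a day short, so dose-timing shifts of under a week can only inflate the average weekly dose

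*SAP*

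**What the plan says.** The regimen is "INCB050465 20 mg QD for 8 weeks followed by 20 mg QW" (SAP section 3). Protocol Table 3 starts the weekly schedule at Week 9 Day 1 and allows reductions, first to "10 mg once weekly" and then to 5 mg once weekly.

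SAP 6.4 Exposure gives two linked definitions for the weekly schedule:

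- Duration in weeks begins "Ceiling of [(date of last dose of INCB050465 during QW schedule" and continues with the subtraction of the first QW dose date, the addition of 1 and division by 7.
- The average weekly dose is "Total reported INCB050465 dose taken during QW schedule (mg) / duration of treatment with INCB050465 for QW schedule (weeks").

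Duration on the daily schedule, in the same section, is last minus first plus 1 day, with no rounding. Both schedules feed Table 3.1 of SAP Appendix A, which is marked for in-text use.

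On timing, Protocol 5.2.4 tells subjects "To make every effort to take doses on schedule". Neither document sets a window for a weekly dose.

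**The concern.** For a subject dosed exactly every 7 days, the quantity to be rounded up is only one day above a whole number. A single day's shortfall between the first and last dose removes that day, and the count drops by a full week while the number of doses stays the same. A delay of up to 6 days changes nothing. The rounding error is thus one-sided.

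Weekly dosing after Week 8 is the new element of the regimen; Protocol 1.4 introduces it to hold response while reducing adverse events. A reader of Table 3.1 will use the average weekly dose to judge how much drug was delivered in that phase. As defined, it can show more than 20 mg/week for someone who took only what was prescribed, and it can hide a missed dose.

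**Working it through.** **Inputs.** Weekly dose 20 mg (SAP section 3); duration and average-dose formulas (SAP 6.4, with the two dates subtracted); expected treatment "approximately 9 months" (Protocol synopsis, estimated duration of participation), taken as about 39 weeks, less 8 weeks of daily dosing, so about 31 weekly doses.

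**Formula.** Let n be the number of weekly doses and k the number of days by which the first-to-last interval differs from 7(n − 1). Then

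weeks = ceiling[(7(n − 1) + k + 1)/7] = n − 1 + ceiling[(k + 1)/7].

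- k = 0: ceiling(1/7) = 1, so weeks = n and the average is 20n/n = 20.0. The SAP formula returns the prescribed dose when dosing is exactly on schedule.
- k = 1 to 6: the ceiling is still 1, so weeks = n and the average is 20.0.
- k = −1 to −6: the ceiling is 0, so weeks = n − 1 and the average is 20n/(n − 1).
- k = 7: the ceiling is 2, so weeks = n + 1 and the average falls. With 8 doses it is 160/9 = 17.8.

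Only the interval matters: a first weekly dose one day late has the same effect as a last dose one day early.

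**Size for an affected subject, all doses at 20 mg (k = −1 to −6).**

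| Doses n | Calculation | mg/week | Excess |
|---|---|---|---|
| 4 | 80/3 | 26.7 | 33% |
| 7 | 140/6 | 23.3 | 17% |
| 10 | 200/9 | 22.2 | 11% |
| 31 | 620/30 | 20.7 | 3.3% |

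**Missed or reduced doses.**

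- Eight scheduled doses, one missed mid-course, last dose 1 day early: 7 × 20 = 140 mg over an interval of 48 days. SAP weeks = ceiling(49/7) = 7, giving 20.0 mg/week. On the unrounded dosing interval, (48 + 7)/7 = 7.86 weeks, giving 17.8.
- Eight doses of 10 mg, last dose 1 day early: 80/7 = 11.4 instead of 10.0. The figure is inflated but below 20.

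**Direction.** For a whole number m, ceiling(m/7) is at most (m + 6)/7. With m = last − first + 1, the SAP denominator never exceeds (last − first + 7)/7. Measured against the dosing-interval duration, the SAP average is therefore never too low.

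**Frequency (assumption).** Let the first and last doses of fully adherent subjects vary independently and uniformly by up to J days.

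- J = 1: 3 of 9 combinations shorten the interval, 33%.
- J = 2: 10 of 25, 40%.
- J = 3: 21 of 49, 43%.

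None give an average below 20. The group mean for J = 1 to 3 is 20.95 to 21.22 mg/week at 8 doses and 20.22 to 20.29 at 31. If every subject keeps a fixed weekday, the share is near zero.

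**The case against.** The arithmetic is not in dispute; its reach is. Five stronger readings are tempting.

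- *Shifts are built into the schedule by the visit window.* Protocol Table 4 lists drug administration under "Every 3 Weeks (± 3 Days"), but that window governs clinic visits. The first weekly dose is at Week 9 Day 1, whereas 3-weekly visits fall at Weeks 4, 7 and 10 (Table 5, footnote b). Most weekly doses are taken away from the clinic. The documents do not support this reading.
- *Some 43% of subjects will be inflated.* That is the top of an assumed range, not an estimate from the documents.
- *The average will exceed 20 mg/week.* This requires the doses to have been taken at 20 mg. Missed doses lower the numerator, and reductions to 10 or 5 mg lower it further.
- *Late dosing never shows.* True only up to 6 days; from 7 days late the average falls.
- *Dose delivery as a whole is misreported.* SAP 6.4 also counts dose reductions and interruptions on the weekly schedule, SAP 6.5 compliance is measured against the prescribed dose, and Listing 2.7.1 gives individual dosing. None of these uses the rounded duration.

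It is also fair to say that the largest percentages need short weekly exposure, and that at the protocol's own planning length the excess is small. All of this limits the point. It does not remove the one-sided error in the formula.

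**Conclusion.** The formula is wrong as written, and minor in consequence. For first-to-last intervals 1 to 6 days short, the reported average weekly dose is too high by a factor n/(n − 1): 33% at 4 doses, 11% at 10 and 3.3% at about 31. Delays of 1 to 6 days do not offset this. Exceeding 20 mg/week depends on dosing at 20 mg with few or no missed doses; otherwise the figure is inflated without necessarily passing 20.

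How many subjects are affected cannot be determined from the documents. The 33% to 43% range rests on uniform variation of ±1 to ±3 days in both dates, and a fixed weekday gives close to none.

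A reader might infer that efficacy or safety conclusions are at risk. They are not: ORR, the futility rule, the adverse event tables and SAP 6.5 compliance do not use this duration. Only the descriptive exposure summary in Table 3.1 changes.

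**What to change.** In SAP 6.4, replace the rounded-up duration with

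QW duration (weeks) = (last QW dose date − first QW dose date + 7)/7, unrounded,

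and use it as the denominator of the average weekly dose. Adding 7 days credits the last weekly dose with its own week, just as adding 1 day credits the last daily dose with its own day.

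At 7 doses of 20 mg this gives 140 × 7/48 = 20.4 mg/week when the last dose is 1 day early, 20.0 on time and 140 × 7/50 = 19.6 when 1 day late. At 31 doses the figures are 20.09, 20.00 and 19.91. Small values above 20 remain, but they are nearly symmetric and reflect the actual spacing. A single weekly dose still counts as 1 week.

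An alternative, round[(last − first)/7] + 1, keeps whole weeks and returns 20.0 for 1-day shifts either way, but it discards small timing differences. The unrounded form is preferable for a dose-intensity measure.

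The cost is one SAP formula and one derived variable in the Table 3.1 programming, with durations shown as non-integer weeks. No new data are needed and trial conduct does not change.

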6.5. Study Drug Compliance

For subjects in the safety population, overall compliance (%) for INCB050465 will be calculated for all subjects as

compliance (%) = $100 \times [\text{total dose actually taken}] / [\text{total prescribed dose}].$

The total prescribed dose is defined as the sum of the doses prescribed by the investigator accounting for dose modifications.

The total actual dose taken will be calculated based on information entered on the drug accountability CRF. If there is dispensed drug that have not been returned yet, the actual dose taken starting from the dispense date of the unreturned drug will be imputed by the dose taken as reported on the dosing CRF.

6.6. Prior and Concomitant Medication

Prior medications and concomitant medications will be coded using the WHO Drug Dictionary. Number and percentage of subjects in the safety population with each prior and concomitant medications will be summarized by WHO drug class and WHO drug preferred term.

7. EFFICACY

Appendix A provides a list of data displays. Sample data displays are included in a separate document.

7.1. Efficacy Hypotheses

Not applicable.

7.2. Analysis of the Primary Efficacy Parameter

7.2.1. Response Assessment

An objective assessment of disease status is required at baseline (screening) using the PET-CT-based response criteria of the Lugano Classification (Cheson et al 2014). Disease status will be subsequently assessed by PET-CT/MRI at Weeks 9, 18, 27, and every 18 weeks thereafter until disease progression.

Sites will use the PET-CT-based response criteria of the Lugano Classification to assess response to treatment locally. Positron emission tomography is required and therefore the criteria for PET-based response should be applied in most circumstances. Computed tomography/MRI-based response criteria are provided for those subjects with PET scans that

cannot be interpreted or who do not have FDG-avid disease. At each postbaseline disease assessment, response by PET will be collected in the eCRF as CMR, PMR, NMR, PMD, or NE; response by CT/MRI will be collected in the eCRF as CR, PR, SD, PD, or NE. Response by PET will be used as the overall response for the assessment if available, otherwise response by CT/MRI will be used as the overall response for the assessment.

All imaging (PET and CT or MRI) will be submitted to the IRC. Imaging data and applicable clinical data will be reviewed and response assessed using the PET-CT-based response criteria of the Lugano Classification (Cheson et al 2014) by independent reviewers as described in the Imaging Charter. At each postbaseline disease assessment, an overall timepoint response, the overall best response (including the date of first response, if applicable), and the overall date of progression (if applicable) for the subject, considering radiographic data and clinical data, will be provided by the oncologist (labeled with "ONCOLOGIST" in the data). These data will be used in the analyses of related response data.

